11.5.2 Objective Response Rate

A secondary efficacy outcome is the Objective Response Rate (ORR). For purposes of this analysis tumor response will be based on the last post TACE liver MRI response recorded for each patient, as determined by the Central Reviewers based on mRECIST criteria. The ORR will be calculated for the ITT Population as the number of patients with a confirmed complete or partial response (based on mRECIST criteria) divided by the number of ITT patients [ORR=(# CR + # PR)/total # patients]. Patients who have discontinued from the study prior to their first post

baseline tumor evaluation will be considered to have progressed for purposes of calculating the ORR for the ITT population. Ninety-five percent confidence intervals will be calculated for the ORR for both treatment groups and for the difference between treatments. The ORR and corresponding 95% confidence intervals will also be calculated for the Evaluable Population. The ORR efficacy analysis will be performed on a locked database that will be unblinded only after all patients have completed the protocol specified treatment phase of the investigation. Treatment comparisons of the ORRs will be performed using Fisher's Exact Test.

In order to assess the robustness of the ORR analysis using the last post TACE MRI response, a sensitivity analysis of the ORR data using the first post TACE MRI response for the ITT population will be performed. In addition, a data poolability analysis will be performed using a multiple logistic regression model including factors for treatment group, investigational site, and an interaction term for treatment group and investigational site for the ITT population. For purposes of this analysis, sites enrolling fewer than 10 patients may be pooled into a single site.

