 - iii. 20% decline from any value at screening
 2. Neutropenia
 3. Alopecia
 4. Hyperpigmentation
 5. Mucositis
- iii. Evaluate Resource Utilization as assessed by:
 1. Length of stay in hospital following each TACE procedure
 2. Number of unscheduled hospitalizations
 3. Length of stay of unscheduled hospitalizations
 4. New or increased use of non-OTC pain medications
 5. New or increased use of antibiotic medications
- iv. Evaluate overall adverse event rates between the treatment groups
- v. Evaluate objective response rates as determined by mRECIST criteria in the treated area (ORR-T)
 1. In this evaluation progression is defined as new/continued tumor growth in the treated area(s) of the liver or extrahepatic spread. New

tumor growth within an area of the liver not previously treated will not be considered progression.

c. Tertiary Objectives

1. Evaluate Time to Untreatable Progression defined as hepatocellular cancer for which further localized treatment by resection, percutaneous ablation, or embolization is not an option, or when there is extrahepatic spread of the cancer

Untreatable progression will be determined by the Central Reviewers during the study treatment and protocol-specified treatment follow up visits. After the final study TACE and associated assessments, untreatable progression will be determined by the treating physician during survival surveillance

2. Explore the relationship between pharmacokinetic (PK) data and patient outcomes including survival, tumor response, and adverse events

3. Inclusion Criteria

Patients must meet all of the following inclusion criteria in order to be entered into the study:

- a. Age 18 or older
- b. Patient has signed informed consent
- c. Patient must have a diagnosis of hepatocellular cancer confirmed by at least one of the following:
 - i. Histological confirmation
 - ii. Magnetic resonance imaging (MRI) result with early enhancement and delayed enhancement washout of at least one solid liver lesion > 1 cm. Patient must also have evidence of cirrhosis or have chronic hepatitis B.
 - iii. Contrast enhanced computed tomography (CT) with early enhancement and delayed enhancement washout of at least one solid liver lesion > 1cm. Patient must also have evidence of cirrhosis or have chronic hepatitis B.
- d. Patient must not be suitable for treatment by resection or percutaneous ablation at time of study entry.

Patients not suitable for ablation due to lesion location may be enrolled

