7.1 Screening (within 4 weeks (+/- 1 week) of first TACE)

Prior to randomization, each patient will have the following performed:

- Obtain informed consent
- Medical history, including demographics and disease history
- Physical exam, including vital signs, height (baseline only) and weight
- Recording of concomitant medications
- ECG
- Urinalysis (Specific Gravity, Protein, Glucose, Blood)

- Baseline laboratory tests
 - CBC (RBC, WBC, Platelet Count, Hemoglobin, Hematocrit, ANC)
 - AST
 - ALT
 - AFP
 - Total Bilirubin
 - Albumin
 - aPTT/PT/INR
 - Alkaline phosphatase
 - Serum creatinine
 - HCG for premenopausal female patients (baseline only)
- ECOG Performance Status evaluation
- Child-Pugh stage calculation
- Cardiac ejection fraction testing. Subsequent cardiac ejection fraction testing during the protocol specified treatment period must use the same method as at screening.
- Baseline MRI (first study MRI) for tumor assessment (including chest and pelvis), reviewed by Central Reviewers
 - MRI of the liver must be done at baseline to assess hepatic tumors. For those sites at which assessment for presence of extrahepatic disease has been done by CT of the chest and pelvis as the facility standard of care, those results are acceptable in place of MRI of the chest and pelvis so that additional imaging is not performed unnecessarily.

If patient meets all the inclusion criteria and none of the exclusion criteria, the patient will be randomized to a treatment group.

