7.3 MRI and Laboratory evaluations following First TACE Cycle

MRIs of the liver, chest and pelvis and laboratory evaluations must be done within 4 weeks (± 1 week) of the first TACE cycle. If the patient received chemoembolization for bilobar disease, the MRIs and laboratory tests must be done within 4 weeks (± 1 week) of the embolization of the second lobe.

Laboratory evaluations will include those listed under screening, at a minimum, and results will be reviewed by the investigator and clinically significant changes from baseline will be reported as adverse events. Additionally, blood samples will be drawn for PK analysis. MRI results of the liver will be reviewed by Central Reviewers. If the patient has experienced a cardiac related adverse event, cardiac ejection fraction testing will be done.

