7.9 Survival follow -up

Patients will be followed from date of first embolization of the first cycle until a date of death is obtained or the patient is lost to follow up. Survival contacts will be attempted every 3 months after completion of final protocol-specified study visit. Contacts may be by visit, telephone, email, or written response, and may be obtained from the patient, medical records, or care givers/family members. Patients may undergo further treatment after the study-specified TACE treatments at the discretion of their physicians, including but not limited to transplant, resection, percutaneous ethanol injection (PEI), radiofrequency ablation (RFA), additional

embolizations, sorafenib or other treatments, including other investigational methods. Patients who have additional embolizations after the three protocol-defined TACE cycles must have the same type of embolization (cTACE or hqTACE) they received during the study. It would be unethical to deny these patients further treatment which might provide benefit, but any and all of the above could affect long term survival and be confounds in the analysis and interpretation of this study data. For this reason treatments and outcomes after the final study TACE will be documented, to the extent possible, during the survival follow-up period, but will not be considered safety or efficacy outcomes in this study, except time to untreatable progression (TTUP). Survival and TTUP will be the only outcomes evaluated after completion of the protocol specified treatment phase of the investigation.

7. Withdrawal of Patients

Patients will be informed that they have the right to withdraw from the study at any time for any reason, without prejudice to their medical care. The investigator also has the right to withdraw patients from the study for any of the following reasons:

- Adverse events, including cardiac ejection fraction <50%
- Progression to extrahepatic disease
- Refusal of treatment
- Patient request
- Inability to complete study procedures
- Lost to follow up
- Non compliance with study requirements

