9.2.2 Reporting Unanticipated Adverse Events and Serious Adverse Events

Any unanticipated adverse event or SAE, including death, due to any cause that occurs during this investigation, whether or not related to the study treatments, must be reported to the Sponsor immediately (not to exceed 24 hours within site notification of the event) in writing via fax or email. The SAE must be completely described on the AE CRF as well as the provided safety report form.

Safety Contact Information:
Primary Safety Contact: [Redacted] [Redacted] [Redacted] [Redacted]
Medical Monitor [Redacted] [Redacted] [Redacted] [Redacted]

10 Tumor Response Assessment

Response will be assessed using mRECIST criteria to evaluate tumor necrosis, and includes assessment of viable tumor, which is defined as uptake of contrast agent in the arterial phase of MRI.

Central Reviewers will evaluate all liver MRIs for tumor response. Two specially trained interventional radiologists will read each blinded liver MRI. In the event that the reviewers do not agree, a third reader will evaluate the imaging, and this will be the official reading for that

evaluation. Determination of whether a patient receives a third TACE cycle will be based on the results of the central readings, and not the individual clinical sites.

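### No rule carries post-baseline chest and pelvis MRI into ORR, ORR-T or treatment-phase TTUP, so a liver responder with new extrahepatic spread would count as a responder

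*Combined protocol and SAP*

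**What the plan says.** **Images acquired.** Section 7.3 requires wider imaging after the first cycle: "MRIs of the liver, chest and pelvis and laboratory evaluations must be done within 4 weeks". Sections 7.5 and 7.7 repeat this for cycles two and three.

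**Images read centrally.** For the same visit, 7.3 says "MRI results of the liver will be reviewed by Central Reviewers", and 7.5 and 7.7 agree. Section 10 says "Central Reviewers will evaluate all liver MRIs for tumor response". Only the screening section is wider: "Baseline MRI (first study MRI) for tumor assessment (including chest and pelvis), reviewed by Central Reviewers".

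**ORR.** Section 11.5.2: "tumor response will be based on the last post TACE liver MRI response recorded for each patient". Its one override to progression is for patients who discontinue before their first post-baseline tumor evaluation.

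**Withdrawal.** The withdrawal section lists "Progression to extrahepatic disease" as a reason and has the reason recorded on the Study Termination form. It does not link that reason to response status.

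**ORR-T.** Objective 2.b.v: "In this evaluation progression is defined as new/continued tumor growth in the treated area(s) of the liver or extrahepatic spread". Section 11.5.5 and Charter 4.3 confine the endpoint to treated liver.

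**TTUP.** Objective 2.c: "Untreatable progression will be determined by the Central Reviewers during the study treatment" and the associated follow-up visits; the treating physician takes over afterwards. In both 2.c and 11.5.6 the event includes extrahepatic spread.

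**The concern.** Metastases that appear outside the liver during treatment are treatment failure under any RECIST-type rule, including the one this protocol adopts. If ORR is scored from the liver read alone, such a patient stays in the numerator whenever the liver lesions have responded. ORR-T is exposed to the same error, and its definition changes between the objectives and the analysis section, so two analysts could produce different results from the same data.

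For TTUP, an extrahepatic event during treatment could be dated late, when the treating physician becomes the assessor. It could also be lost to censoring, because 11.5.6 censors patients without documented untreatable progression.

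**Working it through.** The plan states no rate, sample size or power for ORR, ORR-T or TTUP, so there is no figure to reproduce. The check is a comparison of the text, followed by an illustration of size.

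**1. ORR: follow one patient.** After cycle two the liver MRI shows a partial response and the chest MRI shows a new metastasis.
- Under 7.5 and section 10, the liver MRI goes to the Central Reviewers and is read as a partial response.
- No section says who reads the chest MRI for response or where the result is entered for analysis.
- The investigator may withdraw the patient for extrahepatic progression.
- Under 11.5.2 the last liver response is partial. The override does not apply, because a post-baseline evaluation exists. The patient is a responder.
- Under 10.1.3 a new HCC lesion is progressive disease, with no restriction on site. Under Appendix G (Overall Response) a new lesion means progression whatever the other lesions do. The patient is a non-responder.

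The planned sensitivity analysis changes which post-TACE MRI is used and does not mention chest or pelvis.

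**2. ORR-T: the definitions side by side.**

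| Place | Extrahepatic spread |
|---|---|
| Objective 2.b.v | Counts as progression |
| Section 11.5.5 | Not considered; treated liver areas only |
| Charter 4.3 | Not considered; each lesion is marked as in treated territory or in liver that was not embolized |

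**3. TTUP: task against tools.** Sections 2.c and 11.5.6 give the treatment-phase assessment to the Central Reviewers. Charter 4.2 lets them record complete response, partial response, stable disease, progressive disease or unknown. Charter section 3 blinds them to site assessments and exam dates. The Charter contains no untreatable-progression assessment and does not mention information on whether further local treatment is possible.

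**4. Size for ORR.** A patient is misclassified only with both extrahepatic spread and a complete or partial liver response. Section 11.2 gives N = 255 per arm; every rate below is an assumption.

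*Ceiling.* Let 2-8% of all patients develop spread during treatment, every one of them a liver responder:
- 255 × 0.02 = 5.1
- 255 × 0.08 = 20.4

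This is at most about 5 to 20 patients per arm.

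*Illustration with a different denominator.* Let the liver-only ORR be 40% to 77% (77% is the six-month response reported in the Background for the Italian multisite study), and let a share s of liver responders, 2% to 10%, have spread. Patients moved = 255 × ORR × s; fall in ORR = ORR × s.
- Low end: 255 × 0.40 × 0.02 = 2.0 patients; 0.40 × 0.02 = 0.8 points
- High end: 255 × 0.77 × 0.10 = 19.6 patients; 0.77 × 0.10 = 7.7 points

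*Effect on the comparison*, with assumed liver-only ORRs of 50% and 62% (difference 12 points):

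| s, lower-ORR arm | s, higher-ORR arm | Corrected ORRs | Difference |
|---|---|---|---|
| 2% | 2% | 49.0% vs 60.8% | 11.8 |
| 10% | 10% | 45.0% vs 55.8% | 10.8 |
| 2% | 10% | 49.0% vs 55.8% | 6.8 |
| 10% | 2% | 45.0% vs 60.8% | 15.8 |

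Equal shares change the difference little. Unequal shares change it materially, in either direction.

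**The case against.** The strongest reply is that the documents do not uniformly exclude extrahepatic disease. Baseline chest and pelvis imaging is listed as centrally reviewed (7.1). The Charter puts all study images through central quality control and has every timepoint read, without naming organs. Appendix G tells readers how to measure extrahepatic manifestations and how to judge porta hepatis nodes. Charter 4.2 computes overall response from the last available assessment with no liver qualifier. A reader could conclude that a wider central read was intended.

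That stands as evidence of conflict, and it rules out saying that the readers are barred from seeing these images. It does not supply the missing route. None of these places sends post-baseline chest or pelvis MRI to a response read, while 7.3, 7.5, 7.7, section 10 and 11.5.2 each say liver. The Appendix F acquisition parameters also cover liver MR only.

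It is also fair to say that the change of TTUP assessor is openly prespecified, and that a site-based rule would admit unblinded judgement: section 6 concedes that treating radiologists cannot be blinded, and Appendix G favours central over local reading. Both points limit what the fix should attempt.

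A reader might infer that the extrahepatic parts of ORR-T and TTUP cannot be assessed at all. The documents do not support that. The images are acquired after every cycle, the withdrawal reason is recorded, some extrahepatic disease may be visible on liver MRI, and the treating physician can record TTUP events in follow-up. What is missing is the rule that links these data to the endpoints.

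**Conclusion.** The concern holds as a gap and a contradiction in endpoint definition. As written, no post-baseline chest or pelvis result has a route into ORR, ORR-T or treatment-phase TTUP. The ORR rule conflicts with 10.1.3 and Appendix G, the ORR-T definitions conflict with each other, and the Charter does not equip the Central Reviewers for the TTUP task they are given.

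The size is unknown because the documents give no rate. Under the assumed 2-8%, 5-20 of 255 per arm is a ceiling for ORR misclassification.

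Two further inferences should be resisted. ORR is not overstated in every arm where extrahepatic spread occurs, because a patient with spread and stable or progressive liver disease is already a non-responder. Nor is bias between arms shown: it would require different shares of liver responders with spread, and the documents give no reason to expect that. ORR and ORR-T are secondary, TTUP is tertiary, and the primary survival analysis is untouched. The correction should be made, but it does not threaten the trial's main conclusion.

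**What to change.** In 11.5.2, 11.5.5, 11.5.6 and Charter 4.2-4.3, state that extrahepatic spread documented on the chest and pelvis imaging already required counts, whatever the liver read, as:
- progressive disease, hence non-response for ORR and ORR-T; and
- a TTUP event on the date of that imaging.

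Bring 11.5.2, 11.5.5, 11.5.6 and Charter 4.3 into line with objectives 2.b.v and 2.c and with 10.1.3. State who reads the post-cycle chest and pelvis images and where the result is recorded. Reconcile the TTUP role given to the Central Reviewers with the Charter, which has no procedure for it. Moving the treatability judgement to unblinded sites is a separate and debatable trade-off, and it is not needed here.

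Report the liver-only ORR as a sensitivity analysis so that the effect of the rule is visible.

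**Cost.** Protocol and Charter wording, with no new imaging. The documents describe no form field for post-cycle chest and pelvis findings, so one may have to be added. If only sites read these images, this component is unblinded. Central reading of images already acquired would avoid that, at the price of extra reading work.

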The study will evaluate safety throughout the protocol specified treatment phase of the investigation by assessing adverse events, as well as clinically significant changes from baseline in laboratory values, findings on physical examination including vital signs, ECOG performance

status, and cardiac ejection fraction testing. Concomitant medication usage will also be assessed. Blood samples will be drawn for pharmacokinetic evaluation the morning after the first TACE procedure and at the time of the MRI and laboratory evaluations following the first TACE cycle. In addition, patients who are still hospitalized at least 6 hours following the first PK blood sample collection will have an additional PK blood sample drawn.

6. Randomization and Blinding

Randomization and blinding of treatment identification will be used to reduce potential bias during data collection and evaluation of clinical endpoints. The treatment assignments will be unblinded once all data from the protocol specified treatment phase has been entered into the clinical database, all of the necessary standard data cleaning techniques have been implemented, and the database has been locked.

Once the informed consent has been signed and the patient has met all the study entry criteria, the patient will be considered eligible for randomization. Patients will be randomized to either the cTACE or hqTACE treatment groups in a 1:1 ratio within 1 week of their first scheduled TACE. Randomization schedules will be generated using an adaptive randomization model (based on the algorithm developed by Simon and Pocock). The adaptive model will control the balance of treatment groups within each site and also take into account the following baseline factors which will be weighted based on importance: Child-Pugh Stage (A or B), ECOG performance (0 or 1) status, recurrent disease (yes or no), AFP (<400 ng/mL or ≥400 ng/mL), presence of macrovascular invasion (yes or no), and tumor location (unilobar or bilobar).

Patients will be blinded to the treatment group to which they are assigned. In order to minimize any bias in interpretation of tumor response, the Central Reviewers who assess treatment response will also be blinded to which treatment the patient is receiving. It is not possible for treating radiologists to be blinded to treatment group because the method of embolization is different for the 2 methods of TACE. The primary efficacy outcome of overall survival is unaffected by blinding.

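### ORR and ORR-T are compared with an unadjusted Fisher's exact test although allocation is minimized on six baseline factors within site, so the comparison is valid but conservative

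*Combined protocol and SAP*

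**What the plan says.** - **Test.** Section 11.5.2 compares ORR without covariates or strata: "Treatment comparisons of the ORRs will be performed using Fisher's Exact Test".
- **Outcome.** ORR is a yes/no outcome with the ITT count as denominator: "tumor response will be based on the last post TACE liver MRI response recorded for each patient". Patients who leave before any follow-up tumor evaluation are counted as progressed.
- **Interval.** The same section promises 95% intervals for each arm and for the difference, and names no method for them.
- **Allocation.** Section 6 uses an adaptive scheme of the Pocock-Simon type: "The adaptive model will control the balance of treatment groups within each site and also take into account the following baseline factors". The six factors are Child-Pugh stage, ECOG status, recurrent disease, AFP (cut at 400 ng/mL), macrovascular invasion and unilobar or bilobar disease.
- **The only ORR regression.** It is a poolability check, a "multiple logistic regression model including factors for treatment group, investigational site, and an interaction term for treatment group and investigational site". It contains none of the six factors.
- **Contrast with survival.** Section 11.5.1 plans a supportive Cox model for overall survival with site and every variable in the final allocation model. ORR has no such counterpart.
- **ORR-T.** Section 11.5.5 refers back to the ORR methods, so it inherits the gap.

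**The concern.** Minimization makes the arms more alike on the chosen factors than chance would. If those factors predict response, the true variance of the difference in ORR is smaller than the unadjusted formula assumes. A test that ignores them then rejects less often than its nominal level and loses power. An unadjusted interval for the difference is wider than it needs to be. Fisher's exact test is conservative in any case, because the 2x2 table is discrete. At stake is a missed or imprecisely estimated difference in the first-listed secondary objective and in ORR-T. A false positive is not at stake.

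**Working it through.** **Inputs.** There are 255 patients per arm (section 11.2), allocation is 1:1 (section 5), and alpha is two-sided 0.05 (section 11.1). The documents assume no response rates, so all response rates below are assumptions shown as a range.

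**The plan's own figure.** The only stated sample size is for overall survival.
- Freedman events: (1.960 + 1.036)² × [(1.5 + 1)/(1.5 − 1)]² = 8.98 × 25 = 224.5, so 225.
- Death by 24 months with exponential survival: 1 − 2^(−24/16) = 0.646 and 1 − 2^(−24/24) = 0.500, mean 0.573.
- Patients per arm: 225/(2 × 0.573) = 196.3, which matches the stated 196.
- The enrolled number is 196 × 1.30 = 254.8, so 255.

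There is no ORR power figure to reproduce.

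**Part 1: Fisher's discreteness.** Let X and Y be the responders in each arm, independent binomials with n = 255. The rejection probability is the sum of P(X = x)·P(Y = y) over all tables with p ≤ 0.05. This is exact and describes simple randomization, so minimization plays no role in it.

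True size at a common response rate:

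| Response rate | Fisher | Chi-square |
|---|---|---|
| 10% | 3.57% | 4.92% |
| 30% | 3.98% | 4.97% |
| 40% | 4.18% | 5.17% |
| 50% | 3.75% | 4.63% |

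Power:

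| Response rates | Fisher | Chi-square | Gap (points) |
|---|---|---|---|
| 30% vs 40% | 62.4% | 65.8% | 3.4 |
| 40% vs 50% | 58.7% | 62.0% | 3.3 |
| 50% vs 62% | 75.7% | 78.3% | 2.6 |
| 65% vs 77% | 82.7% | 85.0% | 2.3 |

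**Part 2: ignoring the minimization factors.** Suppose the factors explain a fraction R² of the variance of response and are almost perfectly balanced. The true variance of the difference is then about (1 − R²) times what the unadjusted formula uses. The true size of an unadjusted normal-theory test is about 2Φ(−1.96/√(1 − R²)). For assumed values of R²:
- R² = 0: 5.0%
- R² = 0.05: 2Φ(−2.011) = 4.4%
- R² = 0.10: 2Φ(−2.066) = 3.9%

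A simulation of Pocock-Simon allocation points the same way. Its settings were all assumed: 510 patients, six binary factors of equal weight, 20 sites without site effects, biased coin 0.8, 12,000 trials per setting, and ORR near 45% vs 57%.

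| Odds ratio for response, each factor | Size: Fisher | Size: chi-square | Size: adjusted logistic | Power: Fisher | Power: adjusted logistic |
|---|---|---|---|---|---|
| 1.00 | 4.4% | 5.2% | 5.4% | 77.5% | 80.6% |
| 1.35 | 4.1% | 4.9% | 5.4% | 75.4% | 79.7% |
| 1.65 | 3.6% | 4.4% | 5.2% | 72.1% | 77.4% |

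The chi-square size also falls as the factors become more prognostic. Replacing Fisher with chi-square would therefore cure part 1 but not part 2.

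**The case against.** The case for leaving the plan alone has several sound parts.

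- **Nothing invalid happens.** Fisher's test holds its level, there is no bias, and the primary endpoint is untouched. This stands.
- **The firm numbers do not measure the minimization issue.** A reader might take the 2 to 3 points in part 1 as the price of ignoring the six factors. They are not, because they would arise under simple randomization too. This stands, and it is why the two parts are kept separate.
- **Part 2 has no anchor in the documents.** Nothing in them says how strongly the factors predict mRECIST response. The subset result in the background section concerns a treatment difference with another product. A simulated setting with an odds ratio of 2.23 per factor gave a 10-point gap, but it implies a 2.23⁶ ≈ 123-fold range of odds across patients. Even 1.65 implies 1.65⁶ ≈ 20-fold. These settings show direction, not size.
- **The simulated powers are not size-matched.** The adjusted logistic model rejected 5.2% to 5.4% of the time under the null, and Fisher less than 5%. Part of the power gap is that difference in level.
- **No planned power is thrown away.** A reader might infer that the design bought ORR power and the test wastes it. Section 11.2 powers overall survival only.
- **Fisher's test does not fix the interval.** Section 11.5.2 names no interval method, so only an unadjusted interval, if one is used, would be affected.
- **The plan is consistent.** For survival, too, the main test is unadjusted and the adjusted model is supportive. This weakens the case for making the adjusted ORR model the main analysis. It does not explain why ORR lacks even a supportive one.

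**Conclusion.** The point holds as a low-cost gain in efficiency, not as a flaw in validity. Fisher's discreteness alone puts the true size at 3.6% to 4.2% for common response rates of 10% to 50% with 255 per arm. In the assumed scenarios it costs 2.3 to 3.4 power points against chi-square. Those figures are exact given the response rates, which are assumptions. Ignoring the minimization factors adds conservatism only in so far as they predict response. That further loss cannot be sized from the documents: it is nil if they do not predict response, and it grows with their strength. The clearest gap in the documents is internal. The variables that drive allocation enter a supportive model for survival and no model for ORR or ORR-T.

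**What to change.** Before the unblinding described in sections 6 and 11.5.2, specify the following:

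1. Compare ORR in the ITT population by logistic regression with treatment, the six minimization factors as coded for allocation, and site. State that sites with fewer than 10 patients are pooled for this model. The present pooling wording is optional and limited to the poolability check.
2. Report the standardized risk difference with a 95% interval. This keeps the marginal scale already promised in section 11.5.2. Name the variance estimator and include a finite-sample correction: in the simulation an uncorrected version rejected 5.2% to 5.6% of the time under the null, against a Monte Carlo standard error of √(0.05 × 0.95/12,000) = 0.2 points.
3. State what is done if the model does not converge, for example which terms are dropped and in what order.
4. Use the same model for ORR-T.
5. Keep Fisher's exact test as a sensitivity analysis.

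At a minimum, add this adjusted model as a supportive ORR analysis, to match the Cox model in section 11.5.1.

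The cost is SAP wording and some programming. The factors must be known to randomize a patient, so no new data, visits or patients are needed.
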